#### Exclusion Criteria

1. Age <18 or > 75 years
2. Constipation-predominant IBS.
3. Clinically significant chronic cardiac, pulmonary, hepatic, renal dysfunction or HIV
4. Presence of active malignancy Current evidence of any gastrointestinal disorder such as celiac disease, inflammatory bowel disease, chronic pancreatitis, scleroderma, HIV, small bowel or colonic resection, paraplegia or quadriplegia
5. Current evidence of drug or alcohol abuse as judged by the investigator
6. Allergy to mesalamine or aspirin
7. Investigator perception of patient's inability to comply with the study protocol
8. Unstable psychiatric disease
9. Recent change in gastrointestinal medications

**DESIGN:** Randomized double-blind placebo-controlled.

#### **Study End-points**

Primary: Improvement in self reported overall Bowel Symptom Scores (BSS) after 8 weeks of treatment will be used as the primary endpoint.

Secondary:

- 1) Change in specific bowel symptoms: bowel frequency, bowel consistency, abdominal pain, urgency, and bloating after 8 weeks treatment.
- 2) IBS-QOL at end of treatment

*Definition of a Responder:* Patient who report at least 50% of the weeks of treatment with satisfactory relief (30% or more reduction in symptom) will be designated as responders.

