##### *Bowel Symptom Scale (BSS)*

BSS is a validated IBS outcome measure which consists of 100-mm visual analog scales related to each symptom of IBS (pain/ discomfort, bloating, constipation, diarrhea) and an overall severity scale. All questions contribute equally to the total score, which ranges from 0-400. Similarly reflux disease questionnaire (RDQ) measures change in upper gastrointestinal symptoms before and after treatment.

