##### *IBS-QOL Questionnaire*

The disease-specific IBS-QOL will be used for evaluation of subjects QOL. The IBS-QOL is a validated disease specific quality of life questionnaire for use in patients with IBS. It has 34 items and measures 8 domains found to be relevant to patients with IBS: dysphoria, interference with activity, body image, health worry, food avoidance, social reaction, sexual, and relationships. The IBS-QOL has high internal consistency and high reproducibility. IBS-QOL has been shown to be sensitive to treatment response in patients with IBS.

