##### *Nepean Dyspepsia Index*

The Nepean Dyspepsia Index (NDI) will be used to evaluate how a patient's life and daily activities are affected by their stomach problems.

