#### *Treatment Schedule*

This study will compare mesalamine two (Lialda®) 1.2 gm tablets orally daily to placebo in 68 patients with diarrhea predominant PI-IBS. The patients will be consented and enter into the screening which can last up to 8 weeks. This will be followed by an 8 week treatment period.

Patients will be re-consented to the newest version of the consent form if changes have been made while they are enrolled on the study. The patient may not be rescreened if there is no change in patient's symptoms if they are outside the screening window.

All patients will fill out the following questionnaires:

- 1) The Bowel Symptom Scale (BSS) at the beginning, at 4 weeks and at the end of the study period to assess any change based simply on admission to the trial.
- 2) The BSI-18 at the beginning of the screening period.
- 3) The IBS-QOL at the beginning, at 4 weeks and end of treatment.
- 4) The Nepean Dyspepsia Index at the beginning, 4 weeks and end of treatment as well as during the mail-in/phone call visits. BDQ (Bowel Disease Questionnaire) at screening.

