#### Time Line

##### *Location of Study*

This study will be performed at the University of Utah Hospital and Clinics and the VA Medical Center.

*Time Table of study:* Approximately 1 Years from the start of patient recruitment

Subject recruitment will start immediately upon IRB approval and continue throughout the duration of the study. We estimate that 50% of recruited patients will qualify for enrollment. Sixty-eight patients with diarrhea-predominant or mixed IBS (with diarrhea as predominant symptom) will be enrolled at the rate of 1-2 per week. The estimated dropout rate is 10%, leaving 64 patients to study. This population will include but not be limited to returned missionaries. We have previously worked with missionaries who have high prevalence of PI-IBS.

*Study visits* (Table 1. Figure 1.)

First visit:

Orientation to the study and informed Consent

Inclusion/Exclusion check

History and physical examination,

Questionnaires: BDQ, IBS-QOL, BSI-18, BSS, Nepean Dyspepsia Index (NDI)

Blood and stool tests (not repeated if done in past 6 months unless there has been an alteration in the symptoms)

Collection of stool sample for storage (if consent is given)

Urine pregnancy Test for women of child bearing potential

Instructions to complete 2 week stool diary during 8-week run in period

Second visit:

Flexible sigmoidoscopy/ colonoscopy with biopsy, if indicated (not repeated if performed during last 5 years, results within normal limits and no change in symptoms)

Third visit

Subjects will be randomly assigned to either two Lialda 1.2gm tablets daily or two placebo tablets daily according to a block randomization schedule generated by the statistician. Medicines will be provided by and dispensed at the Pharmacy. Medication may be mailed at patients' convenience and they will be informed on dosing and storage of medication by telephone.

Mail-in/ telephone visit

Patients will be asked to fill BSS IBS-QOL and NDI at week 4 of the 8 week treatment either by mail or on telephone.

Fourth visit

End of treatment- Questionnaires-BSS, IBS-QOL, and NDI and physical examination

Study drug count

Return all unused study drug and the study drug bottle(s)

**Standard of Care vs. Research-Related Procedures:** all procedures for this study are research-related.

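### Bowel frequency, stool consistency and urgency are named secondary outcomes but have no scheduled on-treatment measure, and nothing weekly is collected to support the responder definition

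*Combined protocol and SAP*

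**What the plan says.** Study End-points lists as the first secondary endpoint "Change in specific bowel symptoms: bowel frequency, bowel consistency, abdominal pain, urgency, and bloating after 8 weeks treatment". It then defines a responder: "Patient who report at least 50% of the weeks of treatment with satisfactory relief (30% or more reduction in symptom"). The symptom to which the 30% applies is not named, and the responder is not itself listed as a primary or secondary endpoint.

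Three places set out what is collected on treatment.

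- **Treatment Schedule:** "The Bowel Symptom Scale (BSS) at the beginning, at 4 weeks and at the end of the study period", with IBS-QOL and NDI also at the beginning, week 4 and end of treatment.
- **Study visits, under Time Line:** "Patients will be asked to fill BSS IBS-QOL and NDI at week 4 of the 8 week treatment either by mail or on telephone", and at the fourth visit "End of treatment- Questionnaires-BSS, IBS-QOL, and NDI and physical examination".
- **Study Procedures table:** BSS, IBS-QOL and NDI are marked at week 4 and week 8; the stool diary is marked at Visit 1 only.

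The instruments are described as follows. The BSS has visual analog scales for "each symptom of IBS (pain/ discomfort, bloating, constipation, diarrhea) and an overall severity scale". The IBS-QOL domains are "dysphoria, interference with activity, body image, health worry, food avoidance, social reaction, sexual, and relationships". The NDI asks how patients' "life and daily activities are affected by their stomach problems".

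Under Sample Size, individual symptoms are to be analysed as 0 to 100 scales of the BSS (written BBS there).

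**The concern.** The endpoint list and the collection schedule do not meet. If sites follow the schedule as written, the first secondary endpoint will have matching week 8 data for abdominal pain and bloating only. The other three symptoms describe bowel habit, in a trial of diarrhea-predominant patients whose hypothesis includes improvement in individual symptoms. Values not recorded during treatment cannot be recovered afterwards.

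The endpoint list also disagrees with the analysis text. The BSS scales to be analysed include diarrhea and constipation, which the endpoint does not name, and leave out frequency, consistency and urgency, which it does. Choosing a substitute measure, or a working responder rule, after data are seen would invite selective reporting.

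**Working it through.** The point concerns data collection, so the main check sets endpoint components against instruments. The plan's one calculation reproduces and is not touched. With a difference of 0.25 × 183 = 45.75, an SD of 65, two-sided alpha 0.05 and 80% power, n = 2 × (1.960 + 0.842)² × 65² / 45.75² = 31.7, so 32 per arm. Then 32 / 0.95 = 33.7, so 34 per arm and 68 in total.

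**Step 1: coverage of the five symptoms on treatment**

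| Named symptom | BSS | IBS-QOL (domains) | NDI (as described) |
|---|---|---|---|
| Bowel frequency | no | no | no |
| Bowel consistency | no | no | no |
| Abdominal pain | yes | no | no |
| Urgency | no | no | no |
| Bloating | yes | no | no |

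Matched: 2 of 5. Unmatched: 3 of 5 = 60%.

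**Step 2: other possible sources**

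- Stool diary: two weeks within the run-in. It could give a baseline, but no week 8 value. Its content is not described.
- Bristol Stool Form scale (Methods): named for usual consistency, alongside the IBS subtype definitions, with no visit assigned.
- Bowel Disease Questionnaire: screening only.
- Two-weekly calls (Assessment of Compliance): their stated purpose is medication compliance.

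None of these schedules an on-treatment value for the three symptoms.

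**Step 3: can responder status be derived from what is collected?**

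The rule needs relief in at least 0.50 × 8 = 4 weeks. The BSS is read twice on treatment, at weeks 4 and 8. Suppose relief were taken from the BSS. Its recall period is not given, so let each reading stand for k weeks. Then 2k weeks are observed and 8 − 2k are not. With relief at r of the two readings, the share of weeks with relief lies between rk/8 and (rk + 8 − 2k)/8.

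| k (assumed) | Relief at neither | Relief at one | Relief at both | Classifiable against 50% |
|---|---|---|---|---|
| 1 week | 0–75% | 12.5–87.5% | 25–100% | nobody |
| 2 weeks | 0–50% | 25–75% | 50–100% | only relief at both |
| 4 weeks | 0% | 50% | 100% | everybody |

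Responder status therefore turns on a choice that the documents do not state.

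**The case against.** The strongest reply is that bowel habit is measured. The BSS has diarrhea and constipation scales, read at baseline, week 4 and week 8, and the analysis text uses the individual BSS scales. On that view two sections merely name symptoms differently, and only urgency lacks any arguable scale. This stands in part: the diarrhea scale is a usable proxy. But it is one rating, which gives neither frequency nor consistency separately and says nothing on urgency, and the endpoint names each of them.

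Second, the schedule lists are incomplete, so absence from them proves little. The reflux questionnaire mentioned under the BSS heading appears at no visit. The urine pregnancy test and the fourth-visit physical examination are in the visit list but not marked in the table, while the week 8 storage samples are in the table but not under the fourth visit. Figure 1 and the questionnaire forms are not available to read, and domain names do not reveal the items of a 34-item instrument. This limits the claim to what is scheduled. On the on-treatment questionnaires, however, the three places agree.

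Third, the phone contacts may carry questionnaires, since Treatment Schedule refers to phone call visits in the plural. That wording concerns the NDI only; no relief question is mentioned.

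Fourth, the responder is not a listed endpoint, and nothing says that relief would come from the BSS; patients might report it directly. Both are fair, and this part deserves less weight. A direct report would still need a question and a schedule, and neither is given. The responder is also the only binary efficacy outcome defined, while the analysis text plans chi-squared tests for secondary binary outcomes.

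**Conclusion.** The concern holds, and the plan should be corrected. As scheduled, 3 of the 5 symptoms in the first secondary endpoint have no matching on-treatment measure. If the BSS diarrhea scale is accepted as a proxy for frequency and consistency, urgency alone (1 of 5) is left with nothing. The responder definition needs weekly information that no listed instrument supplies; whether two BSS readings could stand in for it depends on an assumed recall period, with results running from nobody classifiable to everybody.

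The conclusion rests on the schedule and instrument descriptions as written. It is that no measure is scheduled, not that no form exists. The primary endpoint, IBS-QOL, pain, bloating and the sample size are unaffected, which keeps this below a fatal fault.

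**What to change.** First check whether an existing form already collects these items. If so, add it to Treatment Schedule, the visit list and the Study Procedures table.

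If not:

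1. **Symptoms.** Either repeat the 2-week stool diary in treatment weeks 7-8, with the run-in and on-treatment diaries both recording frequency, stool form and urgency; or replace those three symptoms in the endpoint with the BSS diarrhea and constipation scales, which matches the analysis text.
2. **Responder.** Either add one weekly relief question that names its symptom, which the two-weekly calls could carry by asking about each of the two preceding weeks; or define the responder on collected data, for example a reduction of at least 30% from baseline in total BSS (0-400) at week 8.

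The wording-only options cost nothing to collect, but they give up urgency and the sustained-relief idea, and the diarrhea scale remains a proxy. A second diary or a weekly question is a small added burden for patients. Using the existing calls adds no contacts but relies on two-week recall. Whichever is chosen, the endpoint list and the analysis text should name the same measures before outcome data are examined.

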### Mesalamine and PI-IBS

There is strong evidence that PI-IBS is triggered by inflammation and persists because of self-perpetuating immune response: 1) it starts after gastroenteritis, 2) presence of mast cells which induce the innate and adaptive immune systems 3) the increase in pro-inflammatory and decrease in anti-inflammatory cytokines in blood, 4) PI-IBS shares many of the features of lymphocytic colitis (chronic diarrhea, grossly normal endoscopic findings, mucosal inflammation and a benign course).

It is logical that an anti-inflammatory agent will be effective in PI-IBS. Experimental data show that inflammation, even if mild, can lead to persistent changes in gastrointestinal nerve and smooth muscle function, resulting in dysmotility, rectal hypersensitivity and gastrointestinal dysfunction. Research has also shown that functional changes in mice intestine after infection may be reversed using non-selective or selective anti-inflammatory agents administered after recovery from infection Dunlop et al studied the role of oral steroids in reducing inflammation and enterochromaffin cells numbers. Their study demonstrated a significant decrease in the T-lymphocyte number in the lamina propria but was not associated with an improvement in symptoms. A recent study evaluated mesalamine in non-selective patients with IBS. There was improvement in colon histology but no improvement in symptoms. We have shown that there is trend to improvement in QOL with mesalamine.

The purpose of this study is to evaluate the effects of long acting mesalamine (Lialda®) in patients with PI-IBS. We will evaluate gastrointestinal symptoms and IBS specific quality of life (IBS-QOL) before and after treatment with Lialda®

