## **STATISTICAL METHODS, DATA ANALYSIS AND INTERPRETATION:**

### **Sample Size**

The sample size for this trial is based on primary end-point of overall improvement in BSS. A previous IBS treatment trial reported baseline BSS of  $183 \pm 65$ . To detect 25% change in BSS, 32 patients in each group will provide 80% power using two-sided alpha 0.05 comparisons. Assuming 5% drop out rate, we would require a total of 68 patients ( $n=34$  in each group). Assuming proportional estimates for the individual symptoms of IBS, a similar power will be achieved with this sample size.

The Lialda treated group will be compared to the placebo group on improvement in the BBS global symptoms of IBS (continuous scale, range 0 to 400) and BBS individual symptoms of IBS (continuous scales, range 0 to 100). Given the repeated measurements on continuous outcomes, the data will be analyzed with mixed effects linear regression.

Primary analysis will be based on intention to treat. Exploratory analyses assessing "compliers" will also be reported. We will compare the results of placebo and Lialda treated group. The key comparisons between treatment arms will assess changes from baseline to end of treatment using parametric approaches such as the t- test and, when data is highly skewed, nonparametric approaches such as the Wilcoxon test. We note that it is feasible to construct confidence intervals as well as significance tests in the setting of nonparametric comparisons. For some of the secondary efficacy approaches, such as those with binary/ categorical outcomes, follow-up status will be compared between treatment arms using the chi-squared test of the Mantel-Haenszel chi-square for ordered categorical outcomes. Exact versions of these tests will be performed when cell sizes are excessively small.

In addition to the unadjusted primary analyses we will perform exploratory analyses which will use the logistic regression model for binary outcomes, and the linear regression model for continuous outcomes (transformations or categorization may be necessary for the cell count variables). We expect that psychological factors may affect the response to treatment and therefore will do pre-study psychological analysis and will control for them while evaluating response to treatment.

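### The plan does not fix which IBS-QOL quantity decides the secondary endpoint, and nowhere plans to adjust it for baseline IBS-QOL

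*Combined protocol and SAP*

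**What the plan says.** Four places in the combined protocol and SAP bear on IBS-QOL.

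- **Study End-points.** The primary endpoint is worded as an improvement. The first secondary item is worded as a change: "Change in specific bowel symptoms: bowel frequency, bowel consistency, abdominal pain, urgency, and bloating after 8 weeks treatment". The second is "IBS-QOL at end of treatment", with no mention of change or of baseline.
- **Sample Size (under Statistical Methods).** The general rule is: "The key comparisons between treatment arms will assess changes from baseline to end of treatment using parametric approaches such as the t- test", or a Wilcoxon test when data are highly skewed. IBS-QOL is not named. The next paragraph calls the primary analyses unadjusted. It places regression models among the exploratory analyses and mentions control for psychological factors, but not for baseline IBS-QOL.
- **The later paragraph of Statistical Methods that names IBS-QOL.** Because the questionnaire is collected every 4 weeks, a linear mixed model is planned to quantify trends, with a linear divergence between arms given as an example. No week 8 contrast is named, and the role of the baseline value is not stated.
- **Mesalamine and PI-IBS (and similarly the Background).** "We will evaluate gastrointestinal symptoms and IBS specific quality of life (IBS-QOL) before and after treatment".

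Treatment Schedule confirms that IBS-QOL is collected at the beginning, at 4 weeks and at the end of treatment.

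**The concern.** A reader who has to program the IBS-QOL result finds three candidates: the week 8 value, the change from baseline, and a slope or trend from a mixed model. The documents do not say which one decides the endpoint. None of the three, as described, uses the baseline IBS-QOL as a covariate.

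Two things are at stake. The first is precision: the end value ignores the baseline, and the change score over-corrects for it whenever the baseline to week 8 correlation is below 1. The second is freedom to choose the analysis after the data are seen.

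The endpoint is secondary, but it is not marginal. Quality of life is in the Aim and in the efficacy hypothesis under Objectives. The Background also reports that the group's earlier mesalamine trial saw a trend on quality of life and no improvement in symptoms. A quality-of-life claim is therefore a likely product of this trial.

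**Working it through.** **The plan's own figure.** The Sample Size section states "32 patients in each group will provide 80% power using two-sided alpha 0.05 comparisons", for the Bowel Symptom Scale (BSS). Inputs: baseline BSS 183, SD 65, and "To detect 25% change in BSS". The difference is 0.25 × 183 = 45.75 points, or 45.75/65 = 0.70 SD. The normal-approximation formula gives 32 per group with power 80.4% (t-based: 79.1%, n = 33). Then 64/0.95 = 67.4, rounded up to 68. The stated figures reproduce. They concern BSS; no power, SD, effect or correlation is given for IBS-QOL.

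**Inputs for IBS-QOL.** n = 32 per arm is from the plan. Assumed: bivariate normal scores, equal SDs, two-sided 0.05, baseline to week 8 correlation r varied from 0.2 to 0.8, and true effect varied over 0, 0.3, 0.5 and 0.70 SD (the last is the BSS planning effect).

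**Standard errors of the between-arm estimate, in SD units.**
- End value: √(2/32) = 0.25.
- Change: √(2(1 − r) × 2/32). For r = 0.3/0.5/0.7: 0.296, 0.250, 0.194.
- Baseline-adjusted: √((1 − r²) × 2/32). For r = 0.3/0.5/0.7: 0.238, 0.217, 0.179.

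The end-value and change estimates differ by exactly the chance baseline difference between arms. That difference has mean 0 and SD √(2/32) = 0.25.

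**Power at 0.5 SD** (simulation, 100,000 trials per setting):

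| r | End value | Change | Baseline-adjusted |
|---|---|---|---|
| 0.3 | 50% | 38% | 53% (54% by noncentral t) |
| 0.5 | 50% | 51% | 62% |
| 0.7 | 50% | 72% | 78% |

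**Disagreement on p<0.05 between the end-value and change tests:**

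| True effect | r = 0.3 | r = 0.5 | r = 0.7 | r = 0.8 |
|---|---|---|---|---|
| 0 | 7.5% | 8.1% | 8.9% | 9.1% |
| 0.3 SD | 21% | 24% | 32% | 41% |
| 0.5 SD | 31% | 34% | 39% | 45% |
| 0.70 SD | 27% | 23% | 21% | 21% |

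With r = 0.2 included, the range for effects of 0.3–0.70 SD is 19% (0.3 SD, r = 0.2) to 45% (0.5 SD, r = 0.8). Both tests significant in opposite directions: at most 0.05% in any setting run (r up to 0.9).

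**Error rate if either test could be claimed.** P(either) = (P(end value) + P(change) + P(disagree))/2. With no effect and r = 0.5: (4.95% + 4.94% + 8.13%)/2 = 9.0%. Over r = 0.2 to 0.8 the range is 8.4% to 9.6%.

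**Does the planned mixed model remove the problem?** Take a linear slope over weeks 0, 4 and 8, with baseline as an outcome and a free baseline difference. With times centred at −4, 0 and 4, the least-squares slope is (−4·y0 + 0·y4 + 4·y8)/32 = (y8 − y0)/8. For complete data this is the change score divided by 8, so the same precision loss remains.

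**The case against.** The strongest reply is that there is no contradiction. The wording in Study End-points can be read as instrument plus time point, in parallel with the 8-week phrases in the two items above it. The general rule on changes does not mention IBS-QOL, and the paragraph that does mention it plans a mixed model. On that reading the endpoint list names the variable and the statistical section gives the analysis. This stands in part: a reader might infer that the Sample Size section redefines IBS-QOL as a change from baseline, and the documents do not support that. But even if only a time point is meant, the deciding quantity is still not named. The mixed-model paragraph adds a third candidate, offered only as an example.

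A second reply is that the disagreement figures look alarming only for chosen effects and correlations. This also stands. The contrasts have the same expected treatment effect, the disagreement is 7–9% with no effect, and it is 21–27% at the one planning effect in the documents (0.70 SD, for BSS) with r = 0.3–0.8. Disagreement means significant versus not significant, not benefit versus harm.

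Third, an unadjusted comparison is a legitimate choice, and the plan claims no error control for secondary endpoints in a study meant to inform a larger trial. That is fair. It limits the point to an improvement, but gives no reason to forgo one that costs nothing.

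**Conclusion.** The point holds as a free improvement on a secondary endpoint. The deciding IBS-QOL quantity is not fixed, and adjustment for an already collected baseline is not planned. Under the assumed 0.5 SD effect with 32 per arm, the baseline-adjusted contrast has the highest power at each correlation examined. At r = 0.5 it reaches about 62%, against about 50% for either raw comparison. The gain over the end value is small at r = 0.3 (about 54% against 50%), and the gain over change is modest at r = 0.7 (78% against 72%).

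Two stronger readings are not supported. One is that the two raw definitions often give opposite verdicts: how often they disagree depends on an effect and a correlation that the documents do not give, and significant results in opposite directions practically never occur. The other is that the plan as written has a 9% error rate for this endpoint: that figure applies only if either test may be claimed, which no section proposes. The BSS sample size is not affected.

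The calculations take 32 analysed per arm. The separate mismatch between the dropout statements ("Assuming 5% drop out rate, we would require a total of 68 patients" and "The estimated dropout rate is 10%, leaving 64 patients to study") hardly matters here: 68 × 0.90 = 61.2, or 30.6 per arm, gives an end-value standard error of √(2/30.6) = 0.256 instead of 0.25.

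**What to change.** Make three aligned edits.

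1. **Study End-points, secondary item 2:** define it as the between-arm difference in IBS-QOL at week 8, adjusted for baseline IBS-QOL.
2. **Statistical Methods, the paragraph on IBS-QOL and repeated measures:** state that this difference is estimated as the week 8 treatment contrast of the planned linear mixed model, with baseline IBS-QOL as a covariate. Keep the linear-divergence trend as supportive.
3. **Sample Size, the general rule on changes from baseline:** add that raw end-value and raw-change comparisons of IBS-QOL are descriptive.

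With baseline as a covariate, analysing the week 8 value or the change gives the same treatment estimate and p-value, so the ambiguity between those two disappears. The third candidate is settled only if the mixed-model paragraph is edited as well.

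The cost is about one sentence in each place. No new data or visits are needed, because IBS-QOL is already collected at baseline, week 4 and week 8. The only downside is that the raw comparisons can no longer be claimed as the endpoint result.
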